# **APPENDIX 2. CASE SCREENING FORM**

Case screening	ng form
Hospital name:	Study number:
Locality:	Patient screening number:
District:	Date of visit (dd-mmm-yyyy):
Province:	Date illness started (dd-mmm-yyyy):
Demographi	c data
Date of birth (dd-mmm-yyyy): or est years	imated age: in: months or
Height (cm): Weight (kg):	
Sex: Male Female	
If female, is the patient pregnant?   Yes   No	Not sure
If pregnant, provide the date of the last menstrual pe	eriod (dd-mmm-yyyy):
Pre-treatment te	mperature
History of fever in previous 24 h?  Yes  No	
Temperature: °C  Axillary Tympanic [	Rectal Oral
Thick and thin blood smears for estimati	on of P. falciparum parasite counts
Species: P. falciparum P. vivax P.f mixed	d+ non-P.f species
Were species other than P. falciparum present?	Yes No (If yes, patient is not eligible).
Approximate number of P. falciparum asexual para Presence of $1-100$ parasites / $3-6$ white blood cells' eligible )	
Presence of P. falciparum gametocytes?  Yes	No
Has a blood sample for PCR been collected?  Ye	s 🗌 No
Haemoglobin: g/dl Haematocrit:	%
Urinary analysis (pregnancy	test for female patients)
Result of pregnancy test:  Positive  Negative (	If positive, patient is not eligible)
Inclusion cr	riteria

 
age between and months/ye
 
mono-infection with P. falciparum confirminfection)
 
	ned by positive blood smear (i.e. no mixed
• parasitaemia between and and	/μl of asexual forms

 
measured temperature (depending on metho within previous 24 h
 
	d of measurement) or history of fever

 
ability to swallow oral medication
 
	

 
ability and willingness to comply with the st
 
	tudy protocol for the duration of the study

and to comply with the study visit schedule					
• absence of severe malnutrition (defined as per protocol)					
Does the patient meet all the inclusion criteria?	Yes No (If no, patient is not eligible)				
Case screening	form (page 2)				
Exclusion	criteria				
• signs and symptoms of severe or complicate according to WHO criteria (Appendix 1)	ated malaria requiring parenteral treatment				
• mixed or mono-infection with another Pla	smodium species detected by microscopy				

 
severe malnutrition
 
					

 
febrile conditions caused by diseases other than malaria or other known underlying chronic or severe diseases
 
					

 
regular medication which interferes with a
 
	intimalarial pharmacokinetics				

 
history of hypersensitivity reactions or cor
 
	ntraindications to the medicine tested				

 
positive pregnancy test or breastfeeding
 
					

 
unable to or unwilling to take contraceptive
 
	ves.				
Does the patient meet any of the exclusion criteria? Yes No (If yes, the patient is not eligible)					
If yes, please specify the reason for exclusion:					
Patient informed consent and assent					
Consent form signed: Yes No	Patient identity number:				
Assent form signed: Yes No Date (dd-mmm-yyyy):					

# **APPENDIX 3. CASE REPORT FORMS**

Case report form: fo	ollow-up day 0				
Health centre name:	Study number:				
Locality:	Patient identity number:				
District:	Date of visit (dd-mmm-yyyy):				
Province:					
Demographi	c data				
Date of birth (dd-mmm-yyyy): or estingular or estingular years	mated age: in: months or m				
Height (cm): Weight (kg): Sex:	☐ Male ☐ Female				
If female, is the patient pregnant?   Yes   No	Not sure (If yes, patient is not eligible).				
If pregnant, provide the date of the last menstrual I	period (dd-mmm-yyyy):				
Pre-treatment te	mperature				
History of fever in previous 24 h?  Yes  No					
Temperature: °C \sum Axillary \subseteq Tympanic	Rectal Oral				
Thick blood smears for P. falciparum : quantitative parasite counts and qualitative gametocyte counts					
Average number of asexual P. falciparum parasite	s/µl:				
Presence of P. falciparum gametocytes?  Yes No					
Were species other than $P$ . falciparum present? $\square$ Yes $\square$ No (If yes, patient is not eligible).					
If yes, which species? $\square$ P. falciparum $\square$ P. viva	$x \square P.f$ mixed+ non-P.f species				
Has blood sample for PCR been collected?  Yes	s 🗌 No				
Urinary test for antii	malarial drugs				
Test used: Test result:	Positive Negative				
Test used: Test result:	☐ Positive ☐ Negative				
Prior medication					
All prior medication, including natural remedies and homeopathic medicines, taken within the previous 14 days should be reported in this section.  Has the patient taken any prior antimalarial medication?   Yes   No. If yes, please specify below. Either the date of stopping or the 'ongoing' box should be checked.					

Liver Function Tests					
Items	Unit	Value			
1. Total bilirubin	mg/dL				
2. Albumin	g/dL				
3. ALT(SGPT)*	IU/L				
4. AST(SGOT)*	IU/L				

Medicine name (generic name)	Dates	Ongoing (Yes =	Total daily dose and unit (e.g. 400 mg)	Route of administrati on	Indication for use
	Start:				
	Stop:				
	Start:				
	Stop:				
	Start:				
	Stop:				

Case report form: follow-up day 0 (page 2)								
Medication administration								
Name(s) of antimalarial drug(s)	Time of dose (hh:min)	Number of tablets	Did the patient vomit?	Time of vomiting (hh:min)				
			☐ Yes ☐ No					
			☐ Yes ☐ No					
Name(s) of other medicine(s)								
			☐ Yes ☐ No					
			Yes No					

Cas	e report form	: follow-up day	1	
Study number:				
Patient identity number:				
Date of visit (dd-mmm-yyyy):				
	Clinica	l status		
Presence of danger signs or signs or	f severe or co	mplicated malari	ia?  Yes  No	
If yes, perform thick blood smear.				
Temperature: °C  Axillar	y 🔲 Tympani	c Rectal 0	Oral	
Thick blood smears	for estimatio	n of P. falciparu	m parasite counts	S
Average number of asexual P. falc.	iparum parasit	tes/µl:		
Presence of P. falciparum gametoc	ytes?  Yes	☐ No		
Were species other than P. falcipar	um present?	Yes No		
If yes, which species?   P. falcipe	arum 🔲 P. vi	vax P.f mixed	d+ non-P.f species	
	Advers	e events		
Presence of an adverse event?	Yes No			
If yes, name the adverse event:				
Is it a serious adverse event? \( \subseteq \text{ Y} \)	es 🗌 No. If y	es, inform the sp	onsor.	
	Medication a	dministration		
Name(s) of antimalarial drug(s)	Time of dose (hh:min)	Number of tablets	Did the patient vomit?	Time of vomiting (hh:min)
			☐ Yes ☐ No	
☐ Yes ☐ No				
Name(s) of other medicine(s)			1	
, ,			☐ Yes ☐ No	
			☐ Yes ☐ No	

Case report form: follow-up day 2					
Study number:					
Patient identity number:					
Date of visit (dd-mmm-yyyy)	:				
	Clinica	ıl status			
Presence of danger signs or si	gns of severe or co	mplicated malari	ia? 🗌 Yes 🔲 No		
Temperature: °C \sum A:	xillary 🗌 Tympani	ic 🗌 Rectal 🔲 (	Oral		
Thick blood sm	ears for estimatio	n of P. falciparu	m parasite counts	5	
Average number of asexual P	. falciparum parasi	tes/μl:			
Presence of P. falciparum gar	netocytes?  Yes	☐ No			
Were species other than P. fai	lciparum present? [	Yes No			
If yes, which species? $\square$ P. f.	alciparum 🗌 P. vi	vax P.f mixed	d+ non-P.f species		
	Advers	e events			
Presence of an adverse event?	Yes No				
If yes, name the adverse even	t:				
Is it a serious adverse event? [	Yes No. If y	es, inform the sp	onsor.		
	Medication a	dministration			
Name(s) of antimalarial drug(s)	Time of dose (hh:min)	Number of tablets	Did the patient vomit?	Time of vomiting (hh:min)	
			☐ Yes ☐ No		
☐ Yes ☐ No					
Name(s) of other medicine(s)					
			☐ Yes ☐ No		
			☐ Yes ☐ No		

Case report form: follow-up day 3
Study number:
Patient identity number:
Date of visit (dd-mmm-yyyy):
Clinical status
Presence of danger signs or signs of severe or complicated malaria?   Yes   No
Temperature: °C Axillary Tympanic Rectal Oral
Thick blood smears for estimation of P. falciparum parasite counts
Average number of asexual P. falciparum parasites/µl:
Presence of P. falciparum gametocytes?    Yes    No
Were species other than P. falciparum present?  Yes No
If yes, which species? $\square$ P. falciparum $\square$ P. vivax $\square$ P.f mixed+ non-P.f species
Adverse events
Presence of an adverse event?  Yes  No
If yes, name the adverse event:
Is it a serious adverse event?   Yes   No. If yes, inform the sponsor.

Liver Function Tests				
Items	Unit	Value		
1. Total bilirubin	mg/dL			
2. Albumin	g/dL			
3. ALT(SGPT)*	IU/L			
4. AST(SGOT)*	IU/L			

Medication administration					
Name(s) of antimalarial drug(s)	Time of dose (hh:min)	Number of tablets	Did the patient vomit?	Time of vomiting (hh:min)	
			☐ Yes ☐ No		
			☐ Yes ☐ No		

Study number:				
Patient identity number:				
Date of visit (dd-mmm-yyyy):				
	Clinica	l status		
Presence of danger signs or sign	ns of severe or co	mplicated malari	ia?  Yes  No	
History of fever within previous	s 24 h?  Yes	No		
Temperature: °C Axi	llary 🗌 Tympani	c Rectal 0	Oral	
Thick blood smea	rs for estimation	n of P. falciparu	m parasite counts	
Average number of asexual P. f	alciparum parasit	tes/μl:		
Presence of P. falciparum game	etocytes?  Yes	☐ No		
Were species other than P. falci	parum present?	Yes No		
If yes, which species? $\square$ P. fal	ciparum 🗌 P. vi	vax P.f mixed	d+ non-P.f species	
Has a blood sample for PCR be	en collected?	Yes No		
	Adverse	e events		
Presence of an adverse event?	☐ Yes ☐ No			
If yes, name the adverse event:				
Is it a serious adverse event?	Yes No. If ye	es, inform the sp	onsor.	
	Liver Funct	ion Tests		
Items	Unit		Value	
1. Total bilirubin	mg/dL			
2. Albumin	g/dL			
3. ALT(SGPT)*	IU/L			
4. AST(SGOT)*	IU/L			
	Medication ac	dministration		
Name(s) of antimalarial drug(s	Number of tablets	Did the patient vomit?	Time of vomiting (hh:min)	
			☐ Yes ☐ No	
			☐ Yes ☐ No	

Case report form: follow-up day 7

Case report form: follow-up day 14					
Study number:					
Patient identity number:					
Date of visit (dd-mmm-yyyy):					
	Clinica	l status			
Presence of danger signs or signs o	f severe or co	mplicated malari	a?  Yes  No		
History of fever within previous 24	h? Yes	] No			
Temperature: °C Axillary	y 🔲 Tympani	c 🗌 Rectal 🔲 (	Oral		
Thick blood smears	for estimation	n of P. falciparu	m parasite counts	S	
Average number of asexual P. falci	iparum parasit	es/μl:			
Presence of P. falciparum gametoc	ytes?  Yes	□ No			
Were species other than P. falcipar	um present?	☐ Yes ☐ No			
If yes, which species?   P. falcipe	arum 🗌 P. vi	vax P.f mixed	d+ non-P.f species		
Has a blood sample for PCR been of	collected?	Yes No			
	Adverse	e events			
Presence of an adverse event?	les No				
If yes, name the adverse event:					
Is it a serious adverse event? \( \subseteq \text{ Ye}	es 🗌 No. If y	es, inform the sp	onsor.		
I	Medication ac	dministration			
Name(s) of antimalarial drug(s)	Time of dose (hh:min)	Number of tablets	Did the patient vomit?	Time of vomiting (hh:min)	
			☐ Yes ☐ No		
☐ Yes ☐ No					
Name(s) of other medicine(s)					
			☐ Yes ☐ No		
			☐ Yes ☐ No		

Case report form: follow-up day 21					
Study number:					
Patient identity number:					
Date of visit (dd-mmm-yyyy):					
	Clinica	l status			
Presence of danger signs or signs o	f severe or co	mplicated malar	ia? 🗌 Yes 🗌 No		
History of fever within previous 24	h? Yes	No			
Temperature: °C \sum Axillary	y 🗌 Tympani	ic Rectal 0	Oral		
Thick blood smears	for estimation	n of P. falciparu	m parasite counts		
Average number of asexual P. falca	iparum parasi	tes/µl:			
Presence of P. falciparum gametoc	ytes?  Yes	☐ No			
Were species other than P. falcipar	um present? [	Yes No			
If yes, which species? $\square$ P. falcipo	arum 🗌 P. vi	vax 🗌 P.f mixe	d+ non-P.f species		
Has a blood sample for PCR been of	collected?	Yes No			
	Adverso	e events			
Presence of an adverse event?	Yes No				
If yes, name the adverse event:					
Is it a serious adverse event? \( \subseteq \text{ Ye}	es 🗌 No. If y	es, inform the sp	onsor.		
I	Medication a	dministration			
Name(s) of antimalarial drug(s)	Time of dose (hh:min)	Number of tablets	Did the patient vomit?	Time of vomiting (hh:min)	
			☐ Yes ☐ No		
			☐ Yes ☐ No		
Name(s) of other medicine(s)					
			☐ Yes ☐ No		
☐ Yes ☐ No					
			,		
Case report form: follow-up day 28					
Study number:					
Patient identity number:					
Date of visit (dd-mmm-yyyy):					

Clinical status					
Presence of danger signs or	signs o	of severe or co	mplicated malar	ia? 🗌 Yes 🗌 No	
History of fever within prev	ious 24	₄h? ☐ Yes ☐	No		
Temperature: °C Axillary Tympanic Rectal Oral					
Thick blood s	mears	for estimation	n of P. falciparu	m parasite counts	S
Average number of asexual	P. falc	iparum parasi	tes/μl:		
Presence of P. falciparum g	ametoc	eytes?  Yes	☐ No		
Were species other than P. J	falcipar	rum present? [	Yes No		
If yes, which species? $\square P$	. falcip	arum 🗌 P. vi	$vax \square P.fmixe$	d+ non-P.f species	
Has a blood sample for PCF	R been	collected?	Yes No		
		Adverse	e events		
Presence of an adverse ever	nt? 🔲 Y	Yes No			
If yes, name the adverse eve	ent:				
Is it a serious adverse event	? 🔲 Y	es 🗌 No. If y	es, inform the sp	oonsor.	
	Τ	Liver Funct	ion Tests		
Items		Unit		Value	
1. Total bilirubin		mg/dL			
2. Albumin		g/dL			
3. ALT(SGPT)*		IU/L			
4. AST(SGOT)*		IU/L			
	•				
	]	Medication ac	dministration		
Name(s) of antimalarial drug(s)  Time of dose (hh:min)		Number of tablets	Did the patient vomit?	Time of vomiting (hh:min)	
				☐ Yes ☐ No	
				☐ Yes ☐ No	

Case report form: day	( any other d	ay that is not pa	art of regular follo	ow-up)		
Study number:						
Patient identity number:						
Date of visit (dd-mmm-yyyy):						
	Clinica	l status				
Presence of danger signs or signs o	of severe or co	mplicated malari	a?  Yes  No			
History of fever within previous 24	h? Yes	] No				
Temperature: °C  Axillar	y 🔲 Tympani	c 🗌 Rectal 🔲 0	Oral			
Thick blood smears	for estimatio	n of P. falciparu	m parasite counts	S		
Average number of asexual P. falca	iparum parasit	tes/μl:				
Presence of P. falciparum gametoc	ytes?  Yes	☐ No				
Were species other than P. falcipar	um present?	Yes No				
If yes, which species? $\square$ P. falcipa	arum $\square$ P. vi	vax P.f mixed	d+ non-P.f species			
Has a blood sample for PCR been of	collected?	Yes 🗌 No				
	Advers	e events				
Presence of an adverse event?	Yes No					
If yes, name the adverse event:						
Is it a serious adverse event? \( \subseteq \text{ Ye}	es 🗌 No. If y	es, inform the sp	onsor.			
	Medication a	dministration				
Name(s) of antimalarial drug(s)  Time of dose (hh:min)  Number of tablets  Did the patient vomit?  Time of vomiting the patient vomit?						
			☐ Yes ☐ No			
	☐ Yes ☐ No					
Name(s) of other medicine(s)						
			☐ Yes ☐ No			
			☐ Yes ☐ No			
	1		1			

Case report form: follow-up day 35						
Study number:						
Patient identity number:	Patient identity number:					
Date of visit (dd-mmm-yyyy):						
	Clinica	l status				
Presence of danger signs or signs o	f severe or co	mplicated malari	a? 🗌 Yes 🔲 No			
History of fever within previous 24	h? Yes	] No				
Temperature: °C Axillary	y 🗌 Tympani	c 🗌 Rectal 🔲 (	Oral			
Thick blood smears	for estimation	n of P. falciparu	m parasite counts	S		
Average number of asexual P. falci	iparum parasit	es/μl:				
Presence of P. falciparum gametoc	ytes?  Yes	□ No				
Were species other than P. falcipar	rum present?	☐ Yes ☐ No				
If yes, which species? $\square$ P. falcipo	arum 🗌 P. vis	vax P.f mixed	d+ non-P.f species			
Has a blood sample for PCR been of	collected?	Yes No				
	Adverse	e events				
Presence of an adverse event?	Yes No					
If yes, name the adverse event:						
Is it a serious adverse event? \( \subseteq \text{ Ye}	es 🗌 No. If y	es, inform the sp	onsor.			
I	Medication ac	dministration				
Name(s) of antimalarial drug(s)	Time of dose (hh:min)	Number of tablets	Did the patient vomit?	Time of vomiting (hh:min)		
			☐ Yes ☐ No			
☐ Yes ☐ No						
Name(s) of other medicine(s)						
			☐ Yes ☐ No			
			☐ Yes ☐ No			
			l l			

Case	report form	: final day of fo	llow-up (28/42)		
Study number:					
Patient identity number:					
Date of visit (dd-mmm-yyyy)	):				
		Clinical status			
Presence of danger signs or s	igns of sever	e or complicated	l malaria? 🗌 Yes [	No	
History of fever within previous	ous 24 h? 🗌	Yes 🗌 No			
Temperature: °C \subseteq A	xillary 🔲 T	ympanic 🗌 Rec	tal 🗌 Oral		
Thick blood sn	nears for est	imation of P. fa	lciparum parasite	counts	
Average number of asexual F	P. falciparum	parasites/µl:			
Presence of P. falciparum gar	metocytes?	☐ Yes ☐ No			
Were species other than P. fa	lciparum pre	sent? Yes	] No		
If yes, which species? $\square P$ .	falciparum 🗌	P. vivax P	f.fmixed+ non-P.f.	species	
Has a blood sample for PCR	been collecte	ed?  Yes  N	lo		
	A	Adverse events			
Presence of an adverse event	?	No			
If yes, name the adverse even	nt:				
Is it a serious adverse event?	Yes N	lo. If yes, inform	n the sponsor.		
	Medica	tion administra	ation		
Name(s) of antimalarial drug(s)	Time of dose (hh:min)	Number of tablets	Did the patient vomit?	Time of vomiting (hh:min)	
			☐ Yes ☐ No		
			☐ Yes ☐ No		
Name(s) of other medicine(s)					
☐ Yes ☐ No					
			☐ Yes ☐ No		
Urinary	analysis (pi	regnancy test fo	or female patients)		
Patients with a positive p	regnancy tes	st must be follow	wed up for 6–8 we	eks after delivery	
Result of pregnancy test:	Positive \[ \]	Negative D	Date of test (dd-mm	ım-yyyy):	
If the patient is pregnant, follow-up of the pregnancy is required, including: clinical examination of the infant at birth and 6-8 weeks after birth. Please provide comments below. If needed fill in					

the serious adverse ever	nt report form:	
Cas	e report form: final day of follow-up (28/42) (page 2)	
	Overall assessment	
Outcome:		
	adequate clinical and parasitological response	
	early treatment failure	
	late clinical failure	
	☐ late parasitological failure	
	lost to follow-up	
	withdrawn	
Outcome occurred on f	ollow-up day: (e.g. 1, 2, 3, 7, 14,)	
PCR:		
	P. falciparum recrudescence	
	P. falciparum reinfection	
	other species	
	mixed with P. falciparum recrudescence	
	mixed with P. falciparum reinfection	
	unknown	
PCR corrected results:		
	adequate clinical and parasitological response	
	early treatment failure	
	late clinical failure	
	ate parasitological failure	
	lost to follow-up	
	withdrawn	
Reason for withdrawal:		

Other comments:		

## **APPENDIX 4. SERIOUS ADVERSE EVENT REPORT FORM**

Serious adverse event report form			
Health centre name:	Study number:		
Locality:	Patient identity number:		
District:	Date of visit (dd-mmm-yyyy):		
Province:	Follow-up day:		
Demographic dat	a		
Date of birth (dd-mmm-yyyy): or estimate years	ed age: in: months or		
Height (cm): Weight (kg):			
Sex: Male Female			
If female, is the patient pregnant?   Yes   No   No	t sure		
If pregnant, provide the date of the last menstrual period	d (dd-mmm-yyyy):		
Serious adverse ev	ent		
Type of event:			
☐ Death			
Life-threatening			
☐ Hospitalization or prolongation of hospitaliz	ation		
Permanent disability			
Congenital anomaly or birth defect			
Date of occurrence (dd-mmm-yyyy):			
Describe the serious adverse event (include all relevant	laboratory results):		
Describe how the reaction was treated:			

	Serious	adverse ev	ent report for	rm (page 2)	
Comments (e.g. relevions) other laboratory data, reappeared after reinting	whether rea				
		O	Outcome		
Recovered	completely				
☐ Not yet reco	overed				
Recovered y  If patient recovered, p	_	erm consequ		vv).	
1		suspected o	of causing the	serious adverse	event as well as all
concomitant medicines)					
Brand name, batch number, manufacturer name (list suspected medicine first)	Daily dose	Route	Start date	End date	Indications for use

Reporting officer		
Name:		
Qualification:		
Address:		
Phone:		
Fax:		
Email:		
Signature:	Date:	

# APPENDIX 5. GUIDELINES FOR ANALYSIS OF RESULTS

	PCR-uncorr	ected results
End-point for day X (X = 28 or 42)	Cumulative success or failure rate (Kaplan-Meier analysis)	Proportion (per-protocol analysis)
Adequate clinical and parasitological response on day X	Success	Success
Early treatment failure	Failure	Failure
Late clinical failure before day 7	Failure	Failure
Late clinical failure or late parasitological failure on or after day 7	Failure	Failure
Other species infection	Censored day of infection	Excluded from analysis
Lost to follow-up	Censored last day of follow-up according to timetable	Excluded from analysis
Withdrawal and protocol violation	Censored last day of follow-up according to timetable before withdrawal or protocol violation	Excluded from analysis

	PCR-correcte	d results
End-point for day X (X = 28 or 42)	Cumulative success or failure rate (Kaplan-Meier analysis)	Proportion (per-protocol analysis)
Adequate clinical and parasitological response at day X	Success	Success
Early treatment failure	Failure	Failure
Late clinical failure before day 7	Failure	Failure
Late clinical failure or late parasitological failure on or after day 7		
falciparum recrudescence*	Failure	Failure

 
falciparum reinfection*
 
	Censored day of reinfection	Excluded from analysis
other species mixed with falciparum recrudescence	Failure	Failure
other species mixed with falciparum reinfection	Censored day of reinfection	Excluded from analysis

 
other species infection
 
	Censored day of infection	Excluded from analysis

 
undetermined or missing PCR
 
	Excluded from analysis	Excluded from analysis
Lost to follow-up	Censored last day of follow- up according to timetable	Excluded from analysis
Withdrawal and protocol violation	Censored last day of follow- up according to timetable before protocol violation or withdrawal	Excluded from analysis

\* WHO. Methods and techniques for clinical trials on antimalarial drug efficacy: genotyping to identify parasite populations. Geneva, World Health Organization, 2008 (http://www.who.int/malaria/resistance).

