#### 3. Study endpoints

The primary endpoint of the study is D28 PCR and D42 PCR corrected ACPR to assess therapeutic efficacy pyronaridine artesunate for the treatment of uncomplicated falciparum malaria in an area where artemisinin resistant malaria is prevalent.

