#### 6.1.2 Genotyping of malaria parasites

In order to differentiate a recrudescence (same parasite strain) from a newly acquired infection (different parasite strain), a genotype analysis will be conducted. This is based on the extensive genetic diversity among the malaria parasite genes *msp1*, *msp2* and *glurp*. The genotypic profiles of pre- and post-parasite strains are compared.

1

<sup>1WHO. Methods and techniques for clinical trials on antimalarial drug efficacy: genotyping to identify parasite populations. Geneva, World Health Organization, 2008 (http://www.who.int/malaria/resistance).

In addition, samples will be analysed for the presence of the Kelch 13 propeller mutation, a recently discovered molecular marker that is associated strongly with slow parasite clearance and in vitro artemisinin resistance using the Ring Survival Assay (RSA).

The copy number of *P. falciparum* mdr1 gene will also be measured. An increasing copy number is associated with mefloquine (MQ) resistance and treatment failures with ASMQ.

In order to minimize discomfort to the patient due to repeated finger pricks, two to three drops of blood will be collected on filter paper Whatman 3MM during screening or enrolment and each time blood smears are required according to the protocol on and after day 7. Specimens will be labeled anonymously (study number, day of follow-up, date), kept in individual plastic bags with desiccant pouches and protected from light, humidity and extreme temperature until analyzed. When such room temperature conditions are not possible, for example in extremely humid environments where air-conditioning is not available, storage in a refrigerator or freezer will be considered, but great care will be taken to protect samples from frost and moisture. The PCR technique used will be performed by laboratory of Institut Pasteur in Cambodia. Paired filter papers will be used for parasite DNA extraction and genotyping. Unused filter papers will be kept in safe locations until data are eventually validated or for further research needs.

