#### 13. STATISTICAL ANALYSIS:

The primary analysis will be on an 'intention to treat' basis, including all patients enrolled into the study. Primary outcome will be the Kaplan Meier analysis up to day 42 of follow-up. A per protocol analysis will be based on all enrolled patients complying with all inclusion criteria who received a full course of the study drugs. Secondary analyses include the 'adequate parasitological and clinical response' (APCR) at day 28 and day 42. Safety and tolerability measurements will be summarized for the ITT patient population.

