Possible Hy's Law case following the FDA Guidance on Drug Induced Liver Injury: Premarketing Clinical Evaluation dated July 2009 A possible Hy's law case is defined as a subject with any value of ALT or AST above 3xULN together with an increase in bilirubin to a value higher than 2xULN and NOT associated to an ALP value higher than 2xULNA decision on medical and scientific grounds is required to assess whether an immediate notification of an event is warranted in other situations, such as medically important events which are not life-threatening, fatal or cause hospitalization, but could endanger the patient or could rendered necessary an intervention to prevent one of the above conditions to develop.

Remark: Examples of such events are intensive care in the emergency room or at home to treat a bronchospasm; a haematological dyscrasia; convulsions or an asymptomatic increase ALT ( $\geq 10 \text{ x ULN}$ ) not causing hospitalisation, or the development of drug addiction or abuse

TABLE 1: STUDY SCHEDULE

	D0	D1	D2	D3	D4	D7	D14	D21	D28	D35	D42	REPf		olumes
Screening													(ml) per time	
Written informed consent	X												adult	Child
Assign participant ID	X												≥16 yrs	<16yrs
Participant's history	X													
Symptoms checklist	X	X	X	X	X	X	X	X	X	X	X	X		
Vital signs	X	X	X	X	X	X	X	X	X	X	X	X		
Temperature	X	X	X	X	X	X	X	X	X	X	X	X		
General Examination	X	X	X	X	X	X	X	X	X	X	X	X		
Study Drug administration														
PYR-Artesunate	X	X	X											
Laboratory Procedures														
#Malaria blood film	X	X	X	X	X	X	X	X	X	X	X	X	0.5	0.5
HCT or Hb	X	X	X	X	X	X	X	X	X	X	X	X	0.03	0.03
Filter paper blots	X											X	0.3	0.3
FBC	X			X		X	X		X		X	X	1	1
Biochemistry	X			X	_	X	X		X		X	X	1	1
	X					X						X	0.5	0.5

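### Appendix 5 drops late failures without a usable PCR result from the PCR-corrected Kaplan-Meier analysis, although section 13 keeps every enrolled patient; efficacy is overstated unless nearly all of these recurrences are reinfections

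*Protocol*

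**What the plan says.** - **Population and method.** Section 13 sets the primary analysis "on an 'intention to treat' basis, including all patients enrolled into the study" and adds: "Primary outcome will be the Kaplan Meier analysis up to day 42 of follow-up". It does not itself say whether that curve is PCR-corrected.
- **Endpoint.** Section 3 supplies the link: "The primary endpoint of the study is D28 PCR and D42 PCR corrected ACPR". The synopsis agrees.
- **Handling rule.** The PCR-corrected table in Appendix 5 has a group of sub-rows under "Late clinical failure or late parasitological failure on or after day 7". One of them is "undetermined or missing PCR", and both its Kaplan-Meier and its per-protocol cell exclude the patient. Every other row of the Kaplan-Meier column is a success, a failure or a censoring. Even reinfection, loss to follow-up, withdrawal and protocol violation keep their time at risk.
- **Foreseen cases.** The final-day case report form offers an unknown category for the PCR result.
- **Sampling.** Section 6.1.2 collects filter paper at screening or enrolment and "each time blood smears are required according to the protocol on and after day 7". The case report forms from day 7 onward ask at each visit whether a PCR sample was taken. In Table 1 (study schedule), the row "Filter paper blots" is marked only at D0 and in the REP column, which appears to be the visit for a recurrence.

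**The concern.** An analysis that includes all enrolled patients cannot also drop some of them once their outcome has been seen. The dropped group is not a random subset: a patient who stays free of parasites to day 42 can never fall into that row. Each untyped recrudescence that is deleted takes a failure out of the numerator and a patient out of the denominator.

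This bears on the trial's purpose. Section 1 says the study should settle whether a 10% day 42 recrudescence rate among 211 western Cambodian patients was chance or reflects lower efficacy, and that the result will inform national guidelines. At 90% efficacy only about 14 failures are expected, so losing a few of them is visible.

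The schedule conflict adds a route into the deleted row. Section 6.1.1 allows a third microscopist to re-read discordant slides, and section 14 has slides validated by an expert technician. Either could turn a slide positive after the patient has left. If Table 1 were followed, that visit might have no filter paper to genotype.

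**Working it through.** **The plan's own figure.** Section 5 gives 138 patients for 90% efficacy with plus or minus 5 points, and 145 after 5% drop-out. Assuming a two-sided 95% level, n = 1.96² × 0.90 × 0.10 / 0.05² = 138.3, and 138 × 1.05 = 144.9. Both reproduce and are not in dispute. The 5-point half-width is the yardstick below.

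**Inputs.**
- N = 145 (section 5).
- Recrudescence 10%, so 14.5 expected events. This matches the assumed 90% efficacy in section 5 and the earlier local rate in section 1.
- Assumed, because the documents do not give them: 1 to 7 untyped recurrences; 0, 5 or 15 reinfections; recurrences spread over days 14, 21, 28, 35 and 42 as 10, 25, 30, 20 and 15%; no other losses.

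**Case A: no reinfections, every untyped case a recrudescence.** Without censoring, the Kaplan-Meier estimate is a simple proportion. True day 42 efficacy is 1 − 14.5/145 = 90.0%. Deleting k cases gives 130.5/(145 − k):

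| k deleted | Day 42 efficacy | Shift (points) |
|---|---|---|
| 1 | 130.5/144 = 90.6% | +0.6 |
| 2 | 130.5/143 = 91.3% | +1.3 |
| 3 | 130.5/142 = 91.9% | +1.9 |
| 5 | 130.5/140 = 93.2% | +3.2 |
| 7 | 130.5/138 = 94.6% | +4.6 |

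Keeping these patients as failures returns 90.0%. Censoring them at recurrence does not: with k = 5 it gives 93.4%, slightly above deletion.

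**Case B: 5 reinfections, half of the untyped cases recrudescent.** The Kaplan-Meier product, the product over visits of (1 − failures/at risk), gives 89.86% when every PCR is known. Deletion shifts it by +0.3 (k = 1), +0.6 (2), +0.9 (3) and +1.5 (5). For k = 5:

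| Rule for the 5 untyped cases | Day 42 efficacy | Error (points) |
|---|---|---|
| PCR known | 89.9% | – |
| Deleted (Appendix 5) | 91.4% | +1.5 |
| Censored at recurrence | 91.6% | +1.7 |
| Counted as failure | 88.2% | −1.7 |

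The last two rows bracket the truth.

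**Case C: every untyped case a reinfection.** Deletion now removes failure-free time, and the shift is −0.04 (k = 1) to −0.2 (k = 5) with 5 reinfections, and −0.3 for k = 7 with 15. Censoring is exact here, because that is how the table treats a known reinfection.

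**Break-even.** With 5 reinfections and k = 5, the shift is −0.22 if none are recrudescent and +0.13 if 10% are. Linear interpolation gives 0.10 × 0.22/(0.22 + 0.13) = 0.063, so deletion biases upward once more than about 6% of the untyped recurrences are recrudescences.

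**The case against.** Several points on the other side are sound.

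- **The direction is conditional.** A reader might infer that deletion can only raise efficacy. Case C shows otherwise: a known reinfection is not a failure in this table, so deleting an untyped one lowers the estimate slightly. The upward direction needs a recrudescent share above about 6%.
- **Counting all as failure is not neutral.** A reader might infer that this rule removes the bias. In Case B it misses by 1.7 points downward, slightly more than deletion misses upward. It is a lower bound, and which bound leads is a judgement.
- **The conflict needs two sections.** Section 13 does not say PCR-corrected, and the uncorrected table has no such exclusion. PCR-uncorrected response is also a listed endpoint, so these recurrences stay visible in the report. But sections 3 and the synopsis leave a PCR-corrected primary endpoint, and Appendix 5 states how its Kaplan-Meier version is to be run.
- **Low transmission does not settle the share.** Section 1 uses that phrase for the regulator's indication, not to describe the three sites. Nothing in the protocol says what share of recurrences would be recrudescences. The 10% local rate shows only that recrudescence is not rare.
- **Missing samples are not shown.** A reader might infer from Table 1 that late-recognised recurrences will go unsampled. Section 6.1.2 and the case report forms point the other way, and Table 1 is the outlier. The documents support a schedule inconsistency, not a forecast of lost samples.
- **Sensitivity runs often sit in an analysis plan.** That is so, but the deletion rule itself is fixed here and conflicts with section 13.

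Exclusion in the per-protocol column is not in conflict with section 13.

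**Conclusion.** The point stands in conditional form. In the PCR-corrected Kaplan-Meier column, Appendix 5 deletes patients selected by their outcome, and this cannot be reconciled with a primary analysis "including all patients enrolled into the study" once the primary endpoint is read as PCR-corrected.

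The size is about +0.6 points at day 42 per deleted recrudescence, about +0.3 per untyped case if half are recrudescent, and at most about −0.3 in total, in the scenarios run, if none are. One or two untyped cases are small against the planned 5 points; five to seven recrudescences would take up most of it. These figures rest on 145 enrolled, 10% recrudescence, an assumed spread over visits and no other losses. The number of untyped cases is not in the documents, so the realised bias cannot be predicted.

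The Table 1 discrepancy is a separate, certain inconsistency. Its effect on the number of untyped cases is possible but not established.

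**What to change.** 1. In the Kaplan-Meier column of the PCR-corrected table, replace exclusion of untyped late failures with retention. Report day 28 and day 42 PCR-corrected efficacy twice: counted as failure on the day of recurrence (lower bound, which understates efficacy if some are reinfections) and censored on that day (upper bound). State the number of untyped cases beside both, and name in advance which is the headline figure.
2. Leave exclusion in the per-protocol column.
3. State in section 13 that the primary Kaplan-Meier analysis is PCR-corrected, if that is intended, and refer to Appendix 5 for the handling rules.
4. Mark filter paper in Table 1 at D7, D14, D21, D28, D35 and D42, in line with section 6.1.2 and the case report forms, so that a recurrence recognised only at a later slide reading still has a sample for genotyping.

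The cost is one reworded cell, a sentence or two in section 13, six marks in the schedule and one additional analysis run. No patients are added, and the samples are already required by section 6.1.2. The price is that efficacy is shown as a range whenever a PCR result is missing.
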